### 8.3 Dose modifications for lenalidomide based on adverse events during a cycle

CTCAE System/Organ/Class (SOC)	ADVERSE EVENT	ACTION
Blood and lymphatic system disorders	febrile neutropenia associated with fever (temperature $\geq 38.5^{\circ}\text{C}$ )	
 
• Omit lenalidomide dose.
 
• Follow CBC weekly.
 
• If neutropenia has resolved to <math>\leq</math> grade 2 prior to Day 21 and fever has resolved, restart lenalidomide at next lower dose level and continue the cycle through Day 21. If febrile neutropenia is the only toxicity for which a dose reduction is required. G-CSF may be used and the lenalidomide dose maintained.
 

Investigations	If platelet count $<30 \times 10^9/\text{L}$ or ANC $<1.0 \times 10^9/\text{L}$ or ANC $>1.0 \times 10^9/\text{L}$ (up to LLN) with fever (temperature $>38.5^{\circ}\text{C}$ )	
 
• Omit lenalidomide dose.
 
• Follow CBC weekly.
 
• Hold anticoagulation until platelets <math>> 50,000</math>
 
• If platelet count resolves to <math>\leq</math> grade 2 prior to Day 21, restart lenalidomide at next lower dose level and continue the cycle through Day 21.
 
• If neutropenia has resolved to <math>\leq</math> grade 2 prior to Day 21, restart lenalidomide at next lower dose level and continue the cycle through Day 21. If neutropenia is the only toxicity for which a dose reduction is required. G-CSF may be used and the lenalidomide dose maintained.
 

Skin and subcutaneous tissue disorders	Rash maculo papular Grade 2 or 3.	
 
• Omit lenalidomide dose. Follow weekly.
 
• If the toxicity resolves to <math>\leq</math> grade 1 prior to Day 21, restart lenalidomide at next lower dose level and continue the cycle through Day 21.
 

	Any rash Grade 4	
 
• Discontinue lenalidomide. Remove patient from all study treatment.
 
• Go to event monitoring.
 

Nervous system disorders	Peripheral sensory Neuropathy Grade 3	
 
• Omit lenalidomide dose. Follow at least weekly.
 
• If the toxicity resolves to <math>\leq</math> grade 1 prior to Day 21, restart lenalidomide at next lower dose level and continue the cycle through Day 21.
 

CTCAE System/Organ/Class (SOC)	ADVERSE EVENT	ACTION
	Grade 4	
 
Discontinue lenalidomide. Remove patient from all study treatment.
 
Go to event monitoring.
 

Immune system disorders	Allergic reaction Grade 2-3	
 
Omit dose. Follow at least weekly.
 
If the toxicity resolves to <math>\leq</math> grade 1 prior to Day 15 restart at next lower dose level and continue the cycle until Day 21.
 

	Grade 4	
 
Discontinue lenalidomide. Remove patient from all study treatment.
 
Go to event monitoring.
 

Vascular disorders	Thromboembolic event $\geq$ Grade 3	
 
Omit dose and start anticoagulation; restart at investigator's discretion (maintain dose level).
 

	Hyperthyroidism or Hypothyroidism $\geq$ grade 2	
 
Omit lenalidomide for remainder of cycle, evaluate etiology, and initiate appropriate therapy.
 
See Instructions for Initiation of a New Cycle and reduce the dose of lenalidomide by 1 dose level.
 

Other non-hematologic adverse event	Other non-hematologic toxicity $\geq$ Grade 3	
 
Omit lenalidomide dose. Follow at least weekly.
 
If the toxicity resolves to <math>\leq</math> grade 2 prior to Day 21, restart lenalidomide at next lower dose level and continue the cycle through Day 21.
 

Lenalidomide dose modifications for renal impairment developing during treatment, considered not related to lenalidomide

Renal Function	Dose
CrCl 30-60 ml/min	10 mg daily
CrCl $<$ 30 mL/min (not requiring dialysis)	15 mg every 48 hours
CrCl $<$ 30 mL/min (requiring dialysis)	5 mg once daily. On dialysis days, administer the dose after dialysis

\* Located at [REDACTED]

\*\* Use the following to describe actions in the Action column:

- Omit = The current dose(s) for the specified drug(s) during a cycle is skipped. The patient does not make up the omitted dose(s) at a later time
- Hold/Delay = The current dose(s) of all drugs during a cycle is delayed. The patient does make up the delayed dose(s) when the patient meets the protocol criteria to restart drugs.
- Discontinue = The specified drug(s) are totally stopped.

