### 7.1 Treatment Schedule Arm A

Table 7.1			
Induction phase (Cycles 1-12)			
Drug	Route	Dose	Schedule Each cycle is 28 days
Ixazomib	Oral	4 mg	Days 1, 8 and 15
Lenalidomide	Oral	25 mg (if CrCl >60 ml/min)	Days 1-21
		10 mg (if CrCl 30-60 ml/min)	
Daratumumab	IV	16 mg/kg	Cycles 1 and 2: Days 1, 8, 15, 22
			Cycles 3, 4, 5, and 6: Days 1, 15
			Cycles 7 and beyond: Day 1
Dexamethasone	IV/ Oral*	40 mg	Days 1, 8, 15 and 22 Arm A: Cycles 1-12
* On days when daratumumab is given, dexamethasone is given IV over 15 minutes within 1 hour prior to daratumumab			
Maintenance Phase (Cycle 13 + up to 36 months from registration)			
Ixazomib	Oral	4 mg	Days 1, 8 and 15
Daratumumab	IV	16 mg/kg	Day 1
Cycle = 28 days			

NOTE: Once the creatinine clearance is >60 mL/min during the course of the treatment, lenalidomide can be increased to 25 mg.

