### Treatment Schedule Arm B

Table 7.1			
Induction phase (Cycles 1-12)			
Drug	Route	Dose	Schedule Each cycle is 28 days
Ixazomib	Oral	4 mg	Days 1, 8 and 15
Lenalidomide	Oral	25 mg (if CrCl >60 ml/min)	Days 1-21
		10 mg (if CrCl 30-60 ml/min)	
Daratumumab	IV	16 mg/kg	Cycles 1 and 2: Days 1, 8, 15, 22
			Cycles 3, 4, 5, and 6: Days 1, 15
			Cycles 7 and beyond: Day 1
Dexamethasone	IV/ Oral*	40 mg	Days 1, 8, 15 and 22 Arm B: Cycles 1-2
* On days when daratumumab is given, Dexamethasone is given IV over 15 minutes within 1 hour prior to daratumumab			
Maintenance Phase (Cycle 13 + up to 36 months from registration)			
Ixazomib	Oral	4 mg	Days 1, 8 and 15
Daratumumab	IV	16 mg/kg	Day 1
Cycle = 28 days			

NOTE: Once the creatinine clearance is >60 mL/min during the course of the treatment, lenalidomide can be increased to 25 mg.

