## 8.0 Dosage Modification Based on Adverse Events

Strictly follow the modifications in this table for the first **two** cycles, until individual treatment tolerance can be ascertained. Individual drugs can be dose reduced as per the table below depending on the adverse event attribution. If the toxicity is attributable to one drug, only that needs to be dose reduced. If overlapping toxicities are observed, the dose reductions can be alternated between the suspected drugs, starting with the drug most likely related to the adverse event. Thereafter, these modifications should be regarded as guidelines to limit to mild-to-moderate, but not debilitating, side effects. If multiple adverse events are seen, administer dose based on greatest reduction required for any single adverse event observed. Reductions apply to treatment given in the preceding cycle and are based on adverse events observed since the prior dose.

**NOTE: If ixazomib, lenalidomide or daratumumab is discontinued, the patient can continue on the other drugs, unless specified otherwise in the dose modification tables. If all three are discontinued, the patient will go to event monitoring (Section 4.2).**

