**ALERT: ADR reporting may be required for some adverse events (See Section 10)**

8.1 Dose Levels for each drug in the combination  
 (Based on Adverse Events in Tables 8.2-5)

**NOTE:** Toxicities attributable to dexamethasone should lead to dose reduction only for dexamethasone.

Table 8.1 Dose reduction steps				
Step	Ixazomib	Lenalidomide	Daratumumab	Dexamethasone
0	4 mg	25 mg	NA	40 mg
-1	3 mg	15 mg		24 mg
-2	2.3 mg	10 mg		12 mg
-3	Discontinue	5 mg		4 mg
-4	Discontinue	Discontinue		Discontinue

8.11 Instruction for initiation of a new cycle of therapy or restarting therapy after interruption during a cycle for toxicities

A new cycle of treatment may begin on the scheduled Day 1 of a new cycle if:

- The ANC is  $\geq 1000/\mu\text{L}$
- The platelet count is  $\geq 75,000/\mu\text{L}$
- Any other non-hematologic treatment -related adverse event that may have occurred has resolved to  $\leq$ Grade 1 or baseline severity.

If these conditions are not met on Day 1 of a new cycle, the subject will be evaluated weekly and a new cycle of therapy will be held until the toxicity has resolved as described above.

If any drug dosing was halted during the previous cycle and was restarted with a one-level dose reduction without requiring an interruption for the remainder of the cycle, then that reduced dose level will be initiated on Day 1 of the new cycle.

If any drug dosing was omitted for the remainder of the previous cycle or if the new cycle is held due to known hematologic toxicity newly encountered on the scheduled Day 1, then the new cycle will be started with a one-level dose reduction. If a new cycle of therapy cannot be restarted within 4 weeks of the scheduled Day 1 due to non-resolution of drug related toxicities, the patient will be removed from protocol therapy and will go to event monitoring.

→ → Use the NCI Common Terminology Criteria for Adverse Events (CTCAE) version 4.0\* unless otherwise specified ← ←

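### Sections 7.1 and 8.3/8.11 conflict on the lenalidomide dose after drug-related renal impairment: a patient on 25 mg restarts at 15 mg even if creatinine clearance is still 30-60 mL/min, where Table 7.1 gives 10 mg

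*Combined protocol and SAP*

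**What the plan says.** Three parts of the protocol bear on the lenalidomide dose when clearance falls during treatment.

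- **Table 7.1 (both arms, Cycles 1-12).** The dose is 25 mg above 60 mL/min and "10 mg (if CrCl 30-60 ml/min"). Cause is not mentioned. The only note on a change during treatment goes upward: "Once the creatinine clearance is >60 mL/min during the course of the treatment, lenalidomide can be increased to 25 mg".
- **Section 8.3, renal table.** It also gives 10 mg daily at CrCl 30-60, with lower doses below 30. Its heading restricts it: "Lenalidomide dose modifications for renal impairment developing during treatment, considered not related to lenalidomide".
- **Section 8.3, last row, and 8.11.** No row in 8.3 deals with renal impairment related to lenalidomide. At Grade 3 or higher it falls under "Other non-hematologic toxicity". The drug is omitted and, if the event improves to at most "grade 2 prior to Day 21, restart lenalidomide at next lower dose level and continue the cycle through Day 21". If dosing was omitted for the rest of the cycle, 8.11 starts the next one with a one-level reduction. Before that, 8.11 requires this: "Any other non-hematologic treatment -related adverse event that may have occurred has resolved to" Grade 1 or less, or baseline. Neither place mentions clearance.

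On how binding this is, Section 8.0 says "Strictly follow the modifications in this table for the first" two cycles, and then "Thereafter, these modifications should be regarded as guidelines to limit to mild-to-moderate, but not debilitating, side effects".

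**The concern.** Section 15.25 says lenalidomide is eliminated mainly by the kidney, so at a given clearance the suitable dose should not depend on why clearance fell. Yet two patients on 25 mg with the same current CrCl of 30-60 can be given different doses by Section 8: 10 mg if the impairment is called unrelated, 15 mg if it is called related. The higher dose goes to the patient whose kidneys the drug is thought to have harmed.

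What is at stake is patient safety. Section 15.29 describes myelosuppression as dose-dependent, and 15.27 lists renal failure among the very common toxicities of lenalidomide. Attribution is also hard to settle here, because renal insufficiency is a feature of myeloma itself (Section 1.1, Appendix I) and Section 9.9d reports acute renal failure with ixazomib.

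**Working it through.** The plan has no calculated figure on this point to reproduce. The check sets the dosing rules side by side.

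**Inputs.** Lenalidomide steps in Table 8.1: 25, 15, 10, 5 mg, then discontinue. Dose at CrCl 30-60: 10 mg (Table 7.1 and the 8.3 renal table). Dosing days: 1-21. Restart rules: last row of 8.3, and 8.11.

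**Step 1: one level down against the clearance dose at CrCl 30-60.**

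| Dose at event | One level down | Ratio to 10 mg |
|---|---|---|
| 25 mg | 15 mg | 15/10 = 1.5 |
| 15 mg | 10 mg | 10/10 = 1.0 |
| 10 mg | 5 mg | 5/10 = 0.5 |

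The restart exceeds the clearance dose only for a patient on 25 mg.

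**Step 2: cycle of the event.** Suppose Grade 3 is found on Day 15, Days 15-17 are omitted, and dosing restarts on Day 18, leaving 4 dosing days.

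- Rule for related events: 4 x 15 = 60 mg.
- Same omission, restart at the clearance dose: 4 x 10 = 40 mg.
- Renal table applied from Day 15 with no omission: 7 x 10 = 70 mg.

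Each dose after restart is 1.5 times the clearance dose, but omission can bring the cycle total below that of an unrelated case (60 against 70 mg). With only a weekly recheck, the check after Day 15 falls on Day 22, past the last dosing day. Dosing is then omitted for the rest of the cycle, and 8.11 gives 15 mg at the next start.

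**Step 3: a later full cycle.** 21 x 15 = 315 mg against 21 x 10 = 210 mg. This needs CrCl still at 30-60 after the event has returned to Grade 1 or less, or to baseline, as 8.11 requires.

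**Step 4: how wide the 30-60 band is.** Assume the Cockcroft-Gault equation of 3.12 is also used on treatment. At fixed age and weight, CrCl is proportional to 1/creatinine, so CrCl reaches 60 and 30 at (starting CrCl)/60 and (starting CrCl)/30 times the starting creatinine. The starting clearances below are assumed, since the protocol gives no distribution.

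| Assumed starting CrCl (mL/min) | Creatinine multiple at CrCl 60 | Creatinine multiple at CrCl 30 |
|---|---|---|
| 70 | 70/60 = 1.17 | 70/30 = 2.33 |
| 80 | 80/60 = 1.33 | 80/30 = 2.67 |
| 90 | 90/60 = 1.50 | 90/30 = 3.00 |

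Partial recovery of creatinine can therefore leave CrCl at 30-60. The documents do not give the CTCAE grade of these multiples, so this does not show how often a patient who meets a restart condition is still in the band.

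**The case against.** The best defence is Table 7.1. It covers Cycles 1-12, which is all the lenalidomide dosing, it sets the dose by clearance with no condition on cause, and it is not labelled a starting dose. A site that applies it throughout would give no more than 10 mg at CrCl 30-60. This stands in part. A reader might infer from the 8.3 heading that clearance-based dosing is ruled out altogether for related impairment, and the documents do not support that, because the heading limits only its own table. But Table 7.1 does not withdraw the restart rule in 8.3. If it applies throughout, it contradicts the 15 mg restart. If it does not, 15 mg is the only dose stated.

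The split by attribution is also a recognisable design: related toxicity is handled by stopping and restarting lower, unrelated impairment by adjusting to clearance. At onset the related path is the stricter one, because the drug is omitted. That is a good reason to keep the omit and hold rules. It is no reason to restart above the clearance dose.

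The instruction in 8.0 to use the greatest reduction does not settle the matter. It concerns multiple adverse events, and here there is one, which the renal table excludes.

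The safeguards are real: follow-up at least weekly, the 8.11 hold with removal from protocol therapy if a new cycle cannot start within 4 weeks, chemistry every 14 days in cycles 1-3 and every cycle in induction, and discretion after cycle 2. They limit exposure but do not say which dose is right.

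**Conclusion.** The conflict is real and its severity is low. After related renal impairment of Grade 3 or higher, a patient on 25 mg is restarted by 8.3 or 8.11 at 15 mg with no clearance check, while Table 7.1 gives 10 mg at CrCl 30-60 whatever the cause. The size is 1.5-fold per dose, for patients on 25 mg only. The clearest case is the mid-cycle restart, which is allowed at Grade 2 or less. Because the modifications are to be followed strictly in cycles 1-2, the one-level rule has most force then.

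Two stronger readings go too far.

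- A reader might infer a full-cycle excess of 315 against 210 mg. A new cycle needs Grade 1 or less, or baseline, and without the CTCAE renal limits the documents cannot show that such a patient still has CrCl 30-60.
- A reader might infer that below Grade 3 the protocol keeps patients on 25 mg (25/10 = 2.5-fold). There, 8.3 and 8.11 state no clearance-based reduction for related impairment, which is a gap and not an instruction. The difference exists only if Table 7.1 is a starting dose. Read as applying throughout induction, it already gives 10 mg.

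No frequency can be derived, and sample size, significance level and power are untouched.

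**What to change.** Delete the relatedness condition, which is everything after the comma, from the heading of the 8.3 renal table. Then add to 8.3, with a cross-reference in Table 7.1, wording such as:

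*Throughout induction the dose for the current CrCl is a ceiling, whatever the attribution. For related events the omit, hold, reduction and discontinuation rules of 8.3 and 8.11 still apply, including at CrCl below 30, and the renal table alone does not permit restart. Count the one-level reduction from the dose being given at the event, then give the lower of that dose and the clearance dose, with 15 mg every 48 hours counted as 7.5 mg/day.*

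At CrCl 30-60 this gives 10 mg from 25 mg (the lower of 15 and 10), 10 mg from 15 mg, and 5 mg from 10 mg. The cross-reference also settles how Table 7.1 is to be read, and so closes the gap below Grade 3.

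The cost is one heading, a few sentences and a cross-reference. The downside is a lower lenalidomide dose in a few patients, capped at the dose already given at that clearance when the impairment is unrelated.

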## 8.4 Dose modifications for dexamethasone (Dex) based on adverse events during a cycle

CTCAE System/Organ/Class (SOC)*	ADVERSE EVENT	ACTION**
Gastrointestinal disorders	Dyspepsia, gastric or duodenal ulcer, gastritis Grade 1-2 (Symptomatic; altered GI function; medical intervention indicated; limiting instrumental ADL)	Treat with H2 blockers, sucralfate, or omeprazole If symptoms persist despite above measures, decrease dexamethasone dose by 1 dose level
	Dyspepsia, gastric or duodenal ulcer, gastritis $\geq$ Grade 3 (Severely altered GI function; TPN indicated; elective operative or endoscopic intervention indicated; limiting self-care ADL; disabling)	Omit dexamethasone until symptoms adequately controlled Restart one dose level below along with concurrent therapy with H2 blockers, sucralfate, or omeprazole If symptoms persist despite above measures, discontinue dexamethasone and do not resume.
Gastrointestinal disorders	Pancreatitis $\geq$ Grade 3 (Severe pain; vomiting; medical intervention indicated (e.g., analgesia, nutritional support))	Discontinue dexamethasone and do not resume
General disorders and administration site conditions	Edema $\geq$ Grade 3 (limiting function and unresponsive to therapy or anasarca)	Diuretics as needed, and decrease dexamethasone dose by 1 dose level If edema persists despite above measures, decrease dose another dose level Discontinue dexamethasone and do not resume if symptoms persist despite second reduction
Psychiatric disorders	Confusion or Mood alteration $\geq$ Grade 2 (Severe disorientation; limiting self-care ADL)	Omit dexamethasone until symptoms resolve Restart with one dose level reduction If symptoms persist despite above measures, discontinue dexamethasone and do not resume
Musculoskeletal and connective tissue disorders	Muscle weakness $\geq$ Grade 2 Weakness limiting self-care ADL; disabling	Decrease dexamethasone dose by one dose level; if weakness persists despite above measures decrease dose by one additional dose level Discontinue dexamethasone and do not resume if symptoms continue to persist
Metabolism and nutrition disorders	Hyperglycemia Grade 3 or higher ( $>250 - 500$ mg/dL; $>13.9 - 27.8$ mmol/L); hospitalization indicated	Treatment with insulin or oral hypoglycemics as needed If uncontrolled despite above measures, decrease dose by one dose level at a time until levels are satisfactory

\* Located at [REDACTED]

\*\* Use the following to describe actions in the Action column:

- Omit = The current dose(s) for the specified drug(s) during a cycle is skipped. The patient does not make up the omitted dose(s) at a later time
- Hold/Delay = The current dose(s) of all drugs during a cycle is delayed. The patient does make up the delayed dose(s) when the patient meets the protocol criteria to restart drugs.
- Discontinue = The specified drug(s) are totally stopped.

## 8.5 Daratumumab Dose Modification

Dose modification of daratumumab is not permitted, but dose delay is the primary method for managing daratumumab-related toxicities. The attribution of the toxicity to individual drug (s) will be performed by the treating physician.

### 8.51 Daratumumab-Related Toxicity Management

Refer to Section 9.9i for details on management of infusion-related reactions.

ONLY if any of the following criteria are met and the event cannot be ascribed to the other drugs, the daratumumab infusion must be omitted to allow for recovery from toxicity. The criteria for a dose omit are:

- Grade 4 thrombocytopenia or Grade 3 thrombocytopenia with bleeding
- Grade 4 neutropenia, if this is the second occurrence despite growth factor support
- Febrile neutropenia of any grade
- Neutropenia with infection, of any grade
- Grade 3 or higher nonhematologic toxicities with the following exceptions:
  - Grade 3 nausea that responds to antiemetic treatment within 7 days
  - Grade 3 vomiting that responds to antiemetic treatment within 7 days
  - Grade 3 diarrhea that responds to antidiarrheal treatment within 7 days
  - Grade 3 fatigue that was present at baseline or that lasts for <7 days after the last administration of daratumumab
  - Grade 3 asthenia that was present at baseline or that lasts for <7 days after the last administration of daratumumab

If a daratumumab administration does not commence within the prespecified window (Table) of the scheduled administration date, then the dose will be considered a missed dose. Administration may resume at the next planned dosing date.

Table 8.6 Daratumumab-Related Toxicity Management

Cycles	Frequency	Dose Held	Dosing Re-start
1 and 2	Weekly (q1wk)	>3 days	next planned weekly dosing date
3 to 6	Biweekly (q2wks) 	>1 week	next planned biweekly dosing date
7+	Every 4 weeks (Q4W)	>2 weeks	next planned every 4 weeks dosing date

A missed dose will not be made up. Doses of daratumumab may be delayed up to 4 weeks. If a dose is delayed, then the dates of the subsequent doses must be adjusted. Any adverse event deemed to be related to daratumumab and unrelated to lenalidomide, ixazomib or dexamethasone that requires a dose hold of more than 4 weeks will result in permanent discontinuation of daratumumab.

## **9.0 Ancillary Treatment/Supportive Care**

### **9.1 Oral hydration**

Patients are encouraged to drink at least 6 to 8 cups of liquid per day.

### **9.2 Disallowed concurrent treatment**

The following treatments are not permitted during the trial:

- Any other investigational treatment
- Any other systemic anti-neoplastic therapy including, but not limited to, immunotherapy, hormonal therapy or monoclonal antibody therapy.
- Any external beam radiotherapy

Platelet transfusions to help patients meet eligibility criteria are not allowed within 3 days prior to study drug dosing for any dosing day

### **9.3 Nausea and/or vomiting**

Standard anti-emetics including 5-hydroxytryptamine 3 serotonin receptor antagonists are recommended for emesis if it occurs once treatment is initiated; prophylactic anti-emetics may also be considered at the physician's discretion. Dexamethasone should not be administered as an anti-emetic. Fluid deficit should be corrected before initiation of study drug and during treatment.

